2.0 STUDY OBJECTIVES

The objective(s) of this trial are to:

- Compare impact of POAF among two randomized treatment arms; patients with POAF and surgical LAA closure (using AtriClip Gillinov-Cosgrove LAA Exclusion Systems) versus patients with POAF and no surgical LAA closure.
- 2. Evaluate Healthcare resource utilization [i.e. Hospital length of stay (LOS), emergency room and/or hospital re-admissions, and costs associated with specific adverse events that may be related to atrial fibrillation].
- 3. Evaluate long-term outcomes of LAA closure with AtriClip in patients at risk of developing POAF.

Study Number: CP2015-2 CONFIDENTIAL Page 16 of 48

3.0 STUDY ENDPOINTS

Study Endpoints are as follows.

- 1. Perioperative complications associated with AtriClip placement. [Defined as: stroke, major bleeding that requires re-operation and/or transfusion of > 2 U packed red blood cells (PRBC) within any 24-hour period during the first 2 days' post-index procedure, myocardial infarction (MI), or death.]
- 2. Intraoperative successful exclusion of LAA. [Defined as no (0 mm) flow between LAA and LA and ≤ 5 mm LAA remnant by intraoperative TEE with Doppler.]
- 3. Composite event rates between the group of subjects diagnosed with POAF (AtriClip vs no AtriClip) through 365 days' post index procedure and between the group of subjects not diagnosed with POAF (AtriClip vs no AtriClip) through 30 days' post index procedure. Events to be evaluated include: Thromboembolic & Hemorrhagic Events such as cerebrovascular accident (CVA), transient ischemic attack (TIA), peripheral ischemia, hemorrhagic stroke, neurologic bleed, gastrointestinal (GI) bleeds, or other major bleeding event.
- 4. Composite event rates through 365-days post index procedure for all AtriClip patients, regardless of whether the patient develops POAF.
- 5. Healthcare resource utilization variance between groups as related to the composite events above. [Specifically hospital length-of-stay (LOS), reoperation for bleeding, neurologic consults for stroke or TIA, emergency department (ED) visits, and hospital readmissions.]

Study Number: CP2015-2 **CONFIDENTIAL** Page 17 of 48

4.0 INVESTIGATIONAL PLAN

4.1 Overall Study and Design – Subject Disposition Diagram

Study Number: CP2015-2 CONFIDENTIAL Page 18 of 48

Overall Study and Design - Description

All patients who undergo a valve or CABG (structural heart) procedure with direct visual access to the LAA will be eligible to participate based upon consent and evaluation of the inclusion and exclusion criteria defined in this protocol.

The target patient population includes patients at risk of POAF based on the CHA2DS2-VASc and HASBLED scoring.

Patient must meet all inclusion/exclusion criteria (including intra-operative exclusion criteria) before enrollment or randomization.

During the planned structural heart procedure, the intra-operative exclusion criteria will be assessed. If any intra-operative exclusion criteria are met, the subject will be a screen fail and will not be enrolled or randomized.

To execute randomization, at the time of enrollment, subjects will be assigned a sequential identification number at each site and a corresponding sealed envelope which will be opened in the operating room to reveal the treatment group. Subjects will be randomized 2:1 (2 with AtriClip® to 1 with no AtriClip®). Randomization sequences will be generated by the AtriCure Statistician and will be stratified by site. The subject population will be randomized using a blocking scheme for each surgeon to ensure equal and balanced treatment group allocations and to avoid bias with respect to known or unknown subject variables that could affect the outcome of this study.

Post-index procedure, all subjects will be monitored per the hospital standard of care processes for POAF.

Four (4) treatment arms result:

- Surgery with AtriClip (POAF diagnosed / Institution SoC anticoagulation therapy)
- Surgery with AtriClip (No POAF)
- Surgery with no AtriClip (POAF diagnosed / Institution SoC anticoagulation therapy)
- Surgery with no AtriClip (No POAF)

Subjects will be assessed for AEs related to the placement of the AtriClip and will be instructed to notify the PI of any AEs that occur during the study. All subjects that develop POAF during the hospital stay will be followed for approximately 1 year (365 days) post index procedure. In addition, all the subjects in the AtriClip group that do not develop POAF will also be followed for 365-days post index procedure.

4.2 Selection of Study Population

4.2.1 Recruitment

All patients who meet the inclusion criteria will be tracked on a Screening Log. Patients will be provided the IRB approved ICF and will have the opportunity to read, understand, and have their questions answered prior to signing the ICF. If the patient agrees to participate in the study and signs consent, the ICF will be completed. The subject must sign and date the ICF prior to any study-specific procedures being performed. The person reviewing the ICF with the subject will also sign and date the ICF. The subject will be given a copy of the signed ICF to keep.

Study Number: CP2015-2 **CONFIDENTIAL** Page 19 of 48

All subjects who sign the ICF will be documented on a paper Screening and Enrollment Log. Only subjects enrolled into the study will be entered into the EDC.

4.2.2 Enrollment

Patients are considered **enrolled** in the study once they have met Inclusion/Exclusion (including intraoperative exclusion) criteria and are **randomized**.

4.2.3 Inclusion Criteria

Patients satisfying the following criteria will be considered the screening population and will be eligible for participation:

- 1. Age > 18 years male or female.
- 2. Scheduled for any non-mechanical valve and/or CABG (structural heart) procedure where direct access to the LAA is expected.
- 3. No documented preoperative AF.
- 4. CHA2DS2-VASc score of > 2
- 5. HASBLED score of ≥ 2
- 6. Acceptable surgical candidate, including use of general anesthesia.
- 7. Willing and able to provide written informed consent.
- 8. Female patients must be of non-child bearing potential, or have a negative pregnancy test within 7 days prior to index procedure
- 9. Willing and able to return for scheduled follow-up visits.

4.2.4 Exclusion Criteria

Patients satisfying the following criteria will not be eligible for participation:

- 1. Redo cardiac surgery.
- 2. Mechanical heart valve or other anticipated or current requirement for anticoagulation therapy during the post-operative (30 day) period.
- 3. Hypercoagulability conditions that may confound the study.
- 4. Ejection Fraction < 30.
- 5. Left Atrium > 6 cm.
- 6. Severe Diastolic Dysfunction.
- 7. Requires anticoagulation therapy.
- 8. Any known reason that the patient would be unable to tolerate post-surgical anticoagulation therapy.
- 9. Patient had a stroke/cerebrovascular accident (CVA) within previous 30 days prior to signing informed consent.
- 10. Any medical condition or finding for which the Investigator used medical discretion to determine the subject should be excluded.

Study Number: CP2015-2 CONFIDENTIAL Page 20 of 48

- 11. Patient is currently or has participated in a clinical study in the last 30 days prior to signing informed consent. Participation in survey clinical studies with no treatment is not an exclusion criterion.
- 12. Patient has a condition that, in the opinion of the investigator, may jeopardize the patient's well-being, the soundness of this clinical study, or could interfere with provision of informed consent, completion of tests, therapy, or follow-up.

4.2.5 Intra-Operative Exclusion Criteria

Prior to randomization subjects must also meet the following intra-operative criteria. (If criteria are not met, the subject will be a screen fail and will not be eligible to be randomized into the study.)

- 1. Presence of thrombus in the left atrium or LAA.
- 2. LAA tissue is deemed friable or has significant adhesions (as evaluated by the surgeon) near or on the LAA making AtriClip placement overly risky.
- 3. Left atrial appendage is outside the range of manufacturer's recommendations width < 29mm or > 50mm.
- 4. Direct visualization access is not available for AtriClip placement.
- 5. Any medical condition or finding for which the Investigator used medical discretion to determine the subject should be excluded. Any medical condition or finding for which the Investigator used medical discretion to determine the subject should be excluded.

4.2.6 Removal of Subjects from Study

In accordance with the Declaration of Helsinki and the Code of Federal Regulations, a subject has the right to withdraw from the study at any time for any reason without prejudice to his/her future medical care by the physician or the institution. Should a subject (or subject's legally authorized guardian/representative) decide to withdraw; all efforts will be made to collect and report the final visit observations as thoroughly and timely as possible. Subjects who withdraw from the study will not be replaced.

The primary reason for early termination and the date of termination will be recorded in the electronic case report form. Reasons may include:

Investigator Decision

If the subject experiences an adverse event and the Principal Investigator or Medical Monitor believes it is in their best interest to discontinue participation in the study, they will be withdrawn from the study.

Lost to Follow-up

When contact with the subject has been lost without completing the final visit assessment, and every attempt to contact has failed, the subject will be considered lost to follow-up. Final documentation regarding all attempts to contact the subject requesting their return for the final visit should be documented.

Withdrawal of Consent

The subject withdraws consent for participation in the study. Any method of contact with the subject in which they state they no longer want to participate in the study specific activities

Study Number: CP2015-2 **CONFIDENTIAL** Page 21 of 48

constitutes withdrawal of consent. When possible the reason for withdrawal will be documented.

Site Termination or Study Termination

A site or study may be terminated. When this occurs all subjects at the site will be withdrawn and documented as early termination. Reasons for site or study termination may include, but are not limited to the following:

- Administrative Concerns (e.g., inadequate subject enrollment, Investigator/institution noncompliance, change of business strategy, etc.);
- Safety Issues, including those due to non-compliance, which substantially affect the risk to benefit ratio of the study subjects at a site or for the study as a whole;
- Regulatory Body Mandate(s)

Other (which may include):

- Protocol deviation, noncompliance or violation
- Sponsor recommendation
- Device/index procedure failure
- Death

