4.2.7 Follow-up for Early Terminated Subjects

In the event that a subject is eligible, enrolled, and randomized into the study but must early terminate either prior to the index procedure (AtriClip placement) or even after the index procedure; the subject will be followed for 30 days for safety purposes.

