5.0 PROCEDURE

5.1 General Description

Individual centers and investigators will be selected based upon their expertise in the targeted structural heart disease procedures (non-mechanical Mitral Valve Repair/Replacement, Aortic Valve Repair/Replacement, and Coronary Artery By-Pass procedures) as well as proficiency in AtriClip placement.

The term index procedure refers only to the placement/non-placement of the AtriClip (dependent on randomization). All procedures leading up to and after the placement of the AtriClip are considered part of the structural heart procedure and are to be conducted under the discretion of the surgeon in accordance to the hospital's standard of care.

Transesophageal Echocardiography (TEE) with Doppler

Transesophageal echocardiography (TEE) with Doppler must be performed prior to any epicardial surgical intervention. The purpose of the TEE with Doppler is to assess for presence of thrombus. *If a thrombus is present in the left atrium or LAA*, the subject will not be enrolled or randomized into the study and no *AtriClip will be placed*.

The AtriClip LAA Exclusion System must be used only by properly trained and qualified medical personnel in accordance with the Instructions for Use (IFU). Failure to properly follow instructions may result in improper functioning of the device.

Study Number: CP2015-2 CONFIDENTIAL Page 22 of 48

If the subject continues to meet all study eligibility criteria (including intra-operative exclusion criteria), they will be enrolled and randomized. If the subject is randomized to the group to receive the AtriClip LAA Exclusion System placement, the following steps are performed:

Note: A recommended surgical technique is presented below. It is recognized that individual patient anatomic variation, surgical conditions, or surgeon preference may necessitate modifications to the outlined procedures. Regardless, surgeons must adhere to the AtriClip LAA Exclusion System sizing criteria, device selection, and device use instructions as outlined in the IFU.

[figure not shown]

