5.2.2 AtriClip arm

If the subject is randomized to the AtriClip arm, the left atrial appendage should be managed using the AtriClip LAA Exclusion System. The left atrial appendage is typically accessible and exclusion of the Left Appendage by the AtriClip is believed to introduce little time or risk to the primary operation. In the event that, the surgeon deems that the AtriClip device is not able to be utilized for left atrial appendage after randomization, because of anatomical limitations or that it is not feasible or safe to address the LAA, the appendage may be left intact. In the event that a subject is randomized but must early terminate before or after the index procedure; the subject will be followed for 30 days for safety purposes.

Post Index Procedure - Subject Assessment

To assess the subject status with regard to potential bleeding, assessments of hemoglobin and hematocrit shall be performed post index procedure per the hospital's standard of care.

Study Number: CP2015-2 CONFIDENTIAL Page 23 of 48

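### Randomised subjects terminated for an adverse event, deviation, sponsor recommendation or device failure are followed for only 30 days, although the POAF and all-AtriClip composites run to 365 days

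*Combined protocol and SAP*

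**What the plan says.** **Who may be terminated.** Section 4.2.6 covers the adverse-event case: if the investigator or Medical Monitor "believes it is in their best interest to discontinue participation in the study, they will be withdrawn from the study". Its further list of possible reasons includes "Protocol deviation, noncompliance or violation", sponsor recommendation and "Device/index procedure failure". None of these requires the subject to refuse anything.

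**What follows termination.** Section 4.2.7 says of a randomised subject who terminates early, before or after the index procedure, that "the subject will be followed for 30 days for safety purposes". Section 5.2.2 repeats this for the AtriClip arm; section 5.2.1 (no AtriClip) does not. Neither 4.2.7 nor 5.2.2 says whether the 30 days run from termination or from the index procedure.

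**What the endpoints need.** Section 3.0, endpoint 3, is "Composite event rates between the group of subjects diagnosed with POAF (AtriClip vs no AtriClip) through 365 days' post index procedure", with a 30-day horizon for subjects without POAF. Endpoint 4 is the same composite to 365 days in all AtriClip subjects. Section 9.3 allows costs to be summed over 365 days.

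**How the data are analysed.** Section 9.6 keeps randomised subjects in the ITT set if the index procedure was attempted, even if it was aborted. Section 9.7.2 compares events as incidences (Pearson chi-squared or Fisher, possibly logistic regression). Section 9 gives no censoring rule, missing-data method or sensitivity analysis for early termination. Section 9.4 only inflates the sample size for loss to follow-up, and section 9.8 provides for a detailed analysis plan only if needed.

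**The concern.** Randomisation here assigns a single intraoperative act: the clip is placed or it is not. Terminating a subject later does not reverse that act; it only stops the recording of strokes, bleeds and resource use. The 30-day rule therefore cuts outcome data short for a 365-day endpoint with no gain in the exposure being studied.

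The reasons for exit are plausibly related to later outcome. A subject removed after an adverse event or a device failure may not have the same later risk as one who stays. Some reasons are discretionary, in an unblinded trial for which section 12.1 anticipates no independent oversight, and clip failure can occur in only one arm. The missing outcomes may thus be informative and could differ between arms.

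Two other sections bear on this. Section 8.2.2 names, as a category of deviation, subjects who met withdrawal criteria but were not removed, so a site that keeps such a subject in follow-up may be recorded as deviating. And removing subjects for deviations is not needed to obtain a clean analysis set, because section 9.6 already allows a per-protocol population.

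**Working it through.** **1. The plan's sample size, to see which comparison is exposed.** Section 9.4 gives 12.5% vs 6.25% at 30 days, one-sided alpha 0.05, 80% power, 2:1 allocation and a continuity correction. With unpooled variance:

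- n(SOC) = (1.645 + 0.842)² × [0.125 × 0.875 + (0.0625 × 0.9375)/2] / 0.0625² = 219.5
- With the correction: (219.5/4) × [1 + √(1 + 2 × 1.5/(219.5 × 0.0625))]² = 242.9, so 243
- This matches the stated 243 and 485 (728 in total). The allowance for loss is 1 − 728/800 = 9%, the same in both arms.

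This target is reached at day 30, so a 30-day rule leaves it, and the 30-day comparison without POAF, largely intact. The exposed results are the 365-day POAF comparison, the all-AtriClip 365-day rate and 365-day resource use and costs.

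**2. How much follow-up is lost.** For a subject terminated on day t, the unseen time is 365 − (t + 30) = 335 − t days if the clock starts at termination, or 365 − max(t, 30) days if it starts at the index procedure. Exit on day 0 loses 335 days either way. Exit at month 6 (taken as day 180) loses 155 or 185 days.

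**3. Illustration of the effect on the rates.** The documents give no removal rate by arm or reason, so every input here is an assumption except the group sizes 533 and 267 from section 9.4. Let p be the true 365-day risk, equal in both arms and set at 12.5% (the plan's 30-day SOC figure, borrowed for scale). Let w be the share removed, R their risk relative to the others, and s the share of their events that go unseen. Removed subjects stay in the denominator.

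- Risk in those not removed: b = p / (1 − w + wR)
- Observed rate = p − w × R × b × s

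Worked example, w = 9%, R = 2, s = 1: b = 0.125/1.09 = 0.1147; observed = 0.125 − 0.09 × 2 × 0.1147 = 0.1044.

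| Removed, AtriClip vs control | R | s | Observed AtriClip | Observed control | False benefit | Type I error (nominal 5%, two-sided) |
|---|---|---|---|---|---|---|
| 9% vs 9% | 2 | 1 | 10.4% | 10.4% | 0 | 5.0% |
| 5% vs 2% | 2 | 0.5 | 11.9% | 12.25% | 0.35 points | 5.2% |
| 9% vs 3% | 2 | 1 | 10.4% | 11.8% | 1.3 points | 8.7% |
| 9% vs 0% | 3 | 1 | 9.6% | 12.5% | 2.9 points | 22% |

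The type I error is Φ(z − 1.96) + Φ(−z − 1.96), where z is the false difference divided by its standard error at 533 and 267 subjects.

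**4. Reading the table.** Understated rates need no imbalance: the first row loses 2.1 points in each arm, and endpoint 4, which has one arm, is exposed in the same way. A false difference needs unequal removal, or unequal risk among those removed. The table shows only the case of more removal in the AtriClip arm; the reverse imbalance would push the difference the other way.

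**The case against.** A reader might infer that the lost outcomes fall mostly in the AtriClip arm and so favour the device. The documents do not support that. The adverse-event clause, deviations and sponsor recommendation apply to either arm. Section 5.1 defines the index procedure to include non-placement, so section 4.2.7 covers both groups. Only clip failure is specific to AtriClip. Under 2:1 allocation more removed subjects would be AtriClip subjects by count, but that is not a higher proportion.

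Nor do the documents say that a subject whose clip cannot be placed must leave. Section 5.2.2 lets the appendage be left intact, and its next sentence, which begins "In the event that a subject is randomized but must early terminate before or after the index procedure", is a separate condition. The list in section 4.2.6 gives possible reasons to be recorded, not mandatory triggers.

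Other points also carry weight:

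- A subject removed after a stroke or a major bleed has already been counted in an incidence analysis, so those exits cost nothing on the composite.
- That removed subjects would count as event-free is an inference. No section says how they enter the denominator, and section 9.4 sizes the trial on completers.
- The larger illustrations assume that these reasons alone use up the plan's entire 9% loss allowance in the AtriClip arm. The 5% vs 2% case barely moves the type I error.
- Section 9.2 describes a hypothesis-generating pilot.
- The schedule of assessments and the material between sections 6.1 and 8.0 are not in the text available here and may hold follow-up detail.

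These points limit the size of the problem and leave its direction open. They do not remove the conflict: the stated rule stops at 30 days, the endpoints need 365, and the statistical section does not handle the gap. If the schedule does keep these subjects in follow-up, sections 4.2.7 and 5.2.2 need to be reconciled with it.

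**Conclusion.** The point holds as a mismatch between the follow-up rule and the 365-day endpoints. Randomised subjects can be terminated without refusing follow-up, and outcomes that may be informative then go uncollected. The direction and size of any between-arm bias cannot be determined from the documents.

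On the assumed inputs, the false benefit runs from zero with equal removal, through 0.35 points (5% vs 2%), to 2.9 points in a deliberately extreme case. Absolute rates fall by up to 2.1 points even when the arms are balanced (9% removed, twice the risk, all their events unseen). All these figures rest on removed subjects staying in the denominator, which the plan does not state. The powered 30-day comparison and the 30-day comparison without POAF are largely unaffected. The change is worth making because it is cheap, and because outcomes not collected at the time may not be recoverable later.

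**What to change.** 1. In sections 4.2.6, 4.2.7 and 5.2.2, state that an adverse event, protocol deviation, sponsor recommendation or device/index procedure failure does not end endpoint follow-up. Continue contact or record review to each subject's planned horizon (365 days for POAF subjects and all AtriClip subjects) unless consent is withdrawn. This concerns data collection only and leaves clinical decisions as they are.
2. Define when the 30-day safety period starts, for any subject to whom it still applies.
3. Align the deviation category in section 8.2.2, so that keeping such a subject in outcome follow-up is not recorded as a deviation.
4. In section 9.7, analyse subjects as randomised, state how early terminators enter the denominator, and pre-specify a time-to-event or missing-data sensitivity analysis for the 365-day composites. Report early terminations by arm and reason.

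The cost is a wording amendment, follow-up contacts or record review for what should be a small share of subjects, and a little more analysis. The sample size does not change.

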9.4 Sample Size and Power

This is a prospective, multicenter, randomized (2:1), unblinded study conducted in up to 2000 patients at risk of POAF based on the CHA2DS2-VASc and HASBLED scoring at up to 20 USA sites. All patients who undergo a valve or CABG (structural heart) procedure with direct visual access to the LAA will be eligible to participate based upon the inclusion and exclusion criteria defined in this protocol.

A total of up to 2000 patients (approx. 1333 in AtriClip group, approx. 667 in SOC group) at risk of POAF will be enrolled in this study. It is assumed that 40% of the patients will be diagnosed with POAF. A two treatment group one-sided Z-test with continuity correction and an $\alpha = 0.05$ will have 80% power to detect the difference between a medical management (SOC) safety rate of PS = 12.5% and a mechanical exclusion

Study Number: CP2015-2 CONFIDENTIAL Page 35 of 48

(AtriClip) safety rate of PC = 6.25% at 30-days post-op when the sample size (for completers) for patients diagnosed with POAF is 485 in the AtriClip group and 243 in the SOC group (a total sample size of 728). Adjusting for loss to follow-up, 533 patients in the AtriClip group and 267 in the SOC group (a total sample size of 800) are expected to be diagnosed with POAF.

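### Section 4.2.6 has no level between taking part and withdrawing consent, so subjects who stop study activities have no planned collection of composite events to day 365

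*Combined protocol and SAP*

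**What the plan says.** Section 4.2.6 lists withdrawal of consent among the reasons for early termination. Its test is any method of contact in which "they state they no longer want to participate in the study specific activities". Such a statement "constitutes withdrawal of consent. When possible the reason for withdrawal will be documented". No second, partial level is described.

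Three other provisions govern what happens next:

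- On withdrawal, 4.2.6 says that "all efforts will be made to collect and report the final visit observations as thoroughly and timely as possible".
- For a randomized subject who terminates early, 4.2.7 says that "the subject will be followed for 30 days for safety purposes". Section 5.2.2 repeats this.
- Section 4.2.6 adds: "Subjects who withdraw from the study will not be replaced".

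On the outcome side, 4.1 says: "All subjects that develop POAF during the hospital stay will be followed for approximately 1 year (365 days) post index procedure". It sets the same period for AtriClip subjects without POAF. Endpoint 3 in 3.0 and 9.2 compares the composite between arms to day 365 among POAF subjects, and to day 30 among subjects without POAF. Endpoint 4 reports the composite to day 365 in all AtriClip subjects. The components begin "Thromboembolic & Hemorrhagic Events such as cerebrovascular accident (CVA), transient ischemic attack (TIA), peripheral ischemia, hemorrhagic stroke, neurologic bleed" and go on to gastrointestinal and other major bleeds.

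On data sources, the Study Administrative Structure section and 8.1.2 have sites transfer data from medical records or source worksheets to the eCRFs. Section 8.1.1 makes hospital records and investigator files the usual source, and 8.1.11 says that consent to record access is part of the informed consent document.

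**The concern.** A subject who is tired of visits or telephone questionnaires has not necessarily objected to the site reading the chart. Section 4.2.6 gives the site one box for both positions. Once that box is ticked, nothing in the readable text asks the site to look for a stroke, TIA or major bleed later in the year.

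Three features of this trial make the loss matter:

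- It is unblinded. Subjects who know that they have no implant may tire of study activities at a different rate from those who have one, so missing outcomes could depend on arm. Nothing in the documents shows that this will happen, but nothing in the design prevents it.
- Section 9.7.2 compares crude incidence by chi-squared or Fisher's exact test, with logistic regression as an option. No time-to-event method is planned, and 9.6 and 9.7 give no missing-data rule. A subject who leaves event-free at, say, day 60 must be either dropped or counted as event-free for the year, and the plan does not say which.
- Withdrawn subjects are not replaced.

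**Working it through.** **Who has a day-365 outcome to lose.** Section 9.4 plans about 1333 AtriClip and 667 control subjects, with 40% POAF.

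- AtriClip: all 1333 (endpoint 4), of whom 0.40 × 1333 ≈ 533 are also in the POAF comparison (endpoint 3).
- Control with POAF: 0.40 × 667 ≈ 267 (endpoint 3).
- Control without POAF: 667 − 267 = 400. These are compared only to day 30.

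So about 1333 + 267 = 1600 of 2000 subjects have a 365-day composite outcome.

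**What is collected after withdrawal.** Take a subject who withdraws on day 60 (an illustrative day). The final-visit effort is at best one contact at exit, and that visit is itself a study activity the subject has just declined. Section 4.2.7 does not say when its 30 days start:

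- Counted from the index procedure, they are already over, and 365 − 60 = 305 days are uncovered.
- Counted from termination, they end on day 90, and 365 − 90 = 275 days are uncovered.

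Section 10.2.4 does not fill the gap, because follow-up of an unresolved SAE may stop when the subject exits the study.

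**Whether 9.4 can size the loss.** First reproduce the plan's figure: one-sided α = 0.05, 80% power, 12.5% versus 6.25% at 30 days, 2:1 allocation, unpooled variance.

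- Without correction: n(SOC) = (1.645 + 0.842)² × (0.125 × 0.875 + 0.0625 × 0.9375 / 2) / 0.0625² = 219.5.
- With continuity correction: (219.5 / 4) × [1 + √(1 + 3 / (219.5 × 0.0625))]² = 242.9, rounded up to 243. The total is 3 × 242.9 = 728.7, against the stated 728 (485 + 243).

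The plan then writes: "Adjusting for loss to follow-up, 533 patients in the AtriClip group and 267 in the SOC group". The implied loss is 1 − 728/800 = 9.0%, that is 533 − 485 = 48 AtriClip and 267 − 243 = 24 control subjects, 72 in all.

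Power under the same method, with SE = √(0.125 × 0.875 / n₁ + 0.0625 × 0.9375 / n₂) and n₁ the SOC group, is Φ{[0.0625 − 0.5(1/n₁ + 1/n₂)] / SE − 1.645}:

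- 243 and 485 (all 72 lost): 80.0%.
- 267 and 533 (none lost): 83.5%.

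The stated sample size therefore stands, and recovering all 72 subjects would add at most about 3.5 points of power for the 30-day comparison. This measures precision only. It says nothing about bias from arm-dependent loss, and nothing about day 365, for which the documents give neither an event rate nor a withdrawal rate.

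**The case against.** **Existing safeguards.** The final-visit effort and the 30-day follow-up do soften the rule. This stands: the gap lies after those two steps and does not cover all outcome data. Neither reaches day 365.

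**Refusing one activity.** A reader might infer that declining a single questionnaire call or visit ends participation. The text does not say so. It refers to the study-specific activities, most naturally as a whole, and leaves refusal of one activity unclassified. What remains is that sites may classify such refusals differently.

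**Death.** A reader might also infer that 365-day death is lost from the composite. Death is named as an endpoint component only under perioperative complications (endpoint 1). Section 10.2.2 has deaths during the study reported on the Study Exit eCRF. Vital status is worth collecting, but as a separate item.

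**Putting a number on the bias.** It is tempting to run the 72 subjects through scenarios. Completer events are 0.0625 × 485 = 30.3 and 0.125 × 243 = 30.4. The overall difference is (30.4 + 24·f_c)/267 − (30.3 + 48·f_t)/533, where f_c and f_t are the event rates in lost controls and lost AtriClip subjects. The planned 6.25 points becomes 4.6 (f_c = 0, f_t = 12.5%), 3.4 (f_c = 0, f_t = 25%) or 7.4 (f_c = 25%, f_t = 6.25%). The arithmetic is right but answers another question. It uses 30-day rates, much of the 30-day outcome is what 4.2.7 is there to capture, and the 72 are an allowance for loss to follow-up, which 4.2.6 defines separately from withdrawal of consent. The share of loss due to partial refusal is not given.

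**Contradiction between 4.2.6 and 4.2.7.** Section 4.2.7 does not say that its follow-up needs the subject's active cooperation, so the two sections do not strictly collide. They do leave unclear what applies to a subject who has withdrawn all consent.

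**Text not visible.** The consent form and Section 7 are not in the public copy, and use of records after withdrawal depends on consent and authorization wording. The finding is therefore limited to the readable text.

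**Pilot status.** Section 9.2 calls this a hypothesis-generating pilot study. That lowers the stakes, but the remedy is cheap as well.

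**Conclusion.** The point holds as a cheap improvement that should be made. As written, 4.2.6 turns a decision to stop study activities into withdrawal of consent. After a final-visit effort and 30 days of safety follow-up, the readable text provides no collection of composite events to day 365, although endpoints 3 and 4 need it. That medical records could supply many of these events is plausible from the plan's own data sources, but not established. Arm-dependent loss is a possibility created by the open design, not a documented fact. The size at day 365 is unknown; the only firm figure is the ceiling of about 3.5 points of power at 30 days, which does not address bias. The conclusion assumes that no partial-withdrawal provision exists in the consent form or in Section 7.

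**What to change.** In 4.2.6, replace the single rule with two levels recorded on the Study Exit eCRF:

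- (a) The subject stops study visits, calls and questionnaires but permits record review for composite events, readmissions and vital status through day 365.
- (b) The subject withdraws consent for all further data collection.

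Only (b) ends data collection, and data collected before (b) are kept. Add matching wording to the consent form, report the numbers at (a) and (b) by arm, and reconcile 4.2.6 with the 30-day follow-up in 4.2.7 for level (b), including when the 30 days start.

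The cost is protocol and consent wording, one eCRF field, and one record check per level (a) subject at day 365. There are two drawbacks: record review may miss events treated at other hospitals, and a consent amendment may be needed.
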